AE: adverse event; B: bottle; BID: twice daily; Card: blister card; ECG: electrocardiogram; e-diary: electronic diary; IGA-PN: Investigator Global Assessment-Prurigo AE: adverse event; B: bottle; BID: twice daily; Card: blister card; ECG: electrocardiogram; e-diary: electronic diary; IGA-PN: Investigator Global Assessment-Prurigo Nodularis; LFT: liver function test; NA: not applicable; PAS: Prurigo Activity Score; PBI-P: Patient Benefit Index, pruritic versions; PK: pharmacokinetic; PRO: patient-reported outcome; q4wk: every 4 weeks; q8wk: every 8 weeks; SHBG: sex hormone-binding globulin; SOWS: Subjective Opiate Withdrawal Scale; TSH: thyroid stimulating hormone; W: Week; WI-NRS: Worst Itch – Numerical Rating Scale; WOCBP: woman of childbearing potential; ☎: telephone call.

1. **Off-Treatment visit** occurs upon stopping investigational product; regardless of reason. Subjects who elect to go off-treatment prior to 52 weeks of treatment (**premature discontinuation** of investigational product) should be asked to complete the Off-Treatment visit, the 2-week SOWS evaluation, the Last Visit (occurs 14 days after off-treatment visit date), and the End of Study telephone call.
2. Assess **eligibility for down titration** based on criteria of confirmed WI-NRS ≤ 3 and 1 category improvement in PAS lesion healing. If both criteria are met, may discuss the option for a permanent dose reduction to 108 mg BID. Note: if criteria are met, this decision is at the discretion of the Investigator and with the agreement of the subject, but once dose reduction has been initiated no re-escalation is permitted.
3. **Vital signs** are to be obtained after the subject has been seated for at least 5 minutes.
4. **ECGs** are to be performed in triplicate (3 serial ECGs at least 1 minute apart) after the subject has been in the supine position for at least 5 minutes. ECGs are to be transmitted to be read centrally by a core ECG laboratory. The average of the QTcF values from the triplicate ECGs will be performed and presented in a report to be used as the final eligibility assessment for the subject.
5. **Laboratory Evaluations:** Hematology and serum chemistry, LFTs, specified endocrine (TSH all subjects with reflex free T4 if above Upper Limit Normal (ULN) or below Lower Limit Normal (LLN), free testosterone [the fraction not bound to SHBG or albumin] and SHBG for males) and pregnancy if WOCBP (regardless of sexual status); urine pregnancy test to be performed by the local laboratory and confirmed to be negative prior to dispensing investigational product. TSH values above the upper limit of normal (ULN) should be repeated at the next study visit (or approximately 1 month later; whichever occurs first). If TSH remains above the ULN, a Free T4 will be performed on the existing laboratory sample.
6. **AEs** are to be continually assessed starting with the signing of the informed consent. Subjects should continue to record any new AEs or concomitant medication use on the Subject Symptom Log and Subject Medication Log. Site staff are required to remind subjects to bring the logs to each visit (including the telephone contacts). Logs should be reviewed by site staff at every visit prior to re-dispensing (or issuing new logs as needed) to subjects. Final retrieval of the logs, for filing in source records, should occur at the last clinic visit. **Events of special interest should trigger the collection of additional information using the AESI worksheet and documented under the AESI section of the Adverse Event eCRF.** Event details and both subject and investigator narratives should be thoroughly documented in the AESI worksheet and completed under the AESI section of the Adverse Event eCRF.
7. **PROs** (Patient Reported Outcomes) are to be administered by site staff or e-diary as described in the Trialogics User Manual. WI-NRS data will also be collected from the subject via the Trialogics web portal at each clinic visit (beginning at Week 20).
8. **Photography:** To be performed at certain sites only. See the Canfield Quick Reference Guide and User Reference Manual for photography procedures as applicable.
9. The 14-day **SOWS** is to be completed, on the e-diary, at home by the subject. Site staff must change the subject's status to "Off-treatment" on the Trialogics web portal to trigger the launch of the SOWS. Subjects must be instructed to enter SOWS data daily for the 14 days following discontinuation of investigational product regardless of when this occurs (i.e. Week 52 visit or Premature Discontinuation). Data should be reviewed by site staff during the 14-day collection period in order to assess the need for any withdrawal intervention. The e-diary is to be retrieved at the last clinic study visit.

Statistical Analysis Plan (SAP)

IV.

V. STUDY ENDPOINTS

A. Primary Efficacy Endpoint

The primary efficacy endpoint is the difference between the percentage of “Responders” at Week 14 for the NAL ER treatment arm versus the placebo arm. A “Responder” is defined as a subject with a ≥ 4 -point decrease in the 7-day average WI-NRS from baseline to Week 14.

B. Secondary Efficacy Endpoints

Key secondary efficacy endpoints include the following:

- The mean change in ItchyQoL from baseline to Week 14 for the NAL ER treatment arm versus the placebo arm.
- Change in PAS as assessed by the percentage of subjects having a 1-category improvement in the percentage of prurigenous lesions with excoriations/crusts (item 5a) from baseline to Week 14 for the NAL ER treatment arm versus the placebo arm.
- The mean change in sleep disturbance (PROMIS Sleep Disturbance Short Form 8a) from baseline to Week 14 for the NAL ER treatment arm versus the placebo arm.

Other secondary efficacy endpoints include the following:

- The mean change in 7-day average WI-NRS from baseline to Week 14 for the NAL ER treatment arm versus the placebo arm.
- Change in PAS as assessed by the percentage of subjects having a 1-category improvement in the percentage of healed lesions (item 5b) from baseline to Week 14 for the NAL ER treatment arm versus the placebo arm.
- Change in PAS as assessed by the percentage of subjects having a 1-category improvement in the percentage number of lesions (item 2) from baseline to Week 14 for the NAL ER treatment arm versus the placebo arm.
- Change in IGA-PN as assessed by the percentage of subjects having a 1-category improvement in activity for the NAL ER treatment arm versus the placebo arm.
- Change in IGA-PN as assessed by the percentage of subjects having a 1-category improvement in stage for the NAL ER treatment arm versus the placebo arm.
- The proportion of subjects having a PBI-P score of ≥ 1 at Week 14 for the NAL ER treatment arm versus the placebo arm.

C. Pharmacokinetics Endpoint

Nalbuphine plasma concentration (and metabolites as needed).

D. Safety Endpoints

Safety will be assessed based on adverse events (AEs), clinical laboratory measurements, central cardiac core laboratory read-12-lead ECG, vital signs, brief neurological assessments, and physical examinations.

Subjects will also complete the Subjective Opiate Withdrawal Scale (SOWS) on a daily basis for the 2 weeks following the last dose of investigational product, whenever that occurs and regardless of the reason (unless consent is withdrawn).

An independent Data Safety Monitoring Board will periodically review safety data.

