9 INVESTIGATIONAL PLAN

9.1 Overall Study Design and Plan

9.1.1 Description

This is a randomized, double-blinded, placebo-controlled, 2-arm study, with an open-label extension period following double-blind treatment, to investigate the anti-pruritic efficacy and safety of NAL ER tablets. Eligible subjects will be randomized to NAL ER (2-week titration followed by 162 mg BID for 12 weeks) or matching placebo (14 weeks duration), with the primary endpoint evaluation at Week 14. If permanent discontinuation of investigational product occurs anytime between Day 1 and the Week 14 visit, the subject must be asked to complete the Off-Treatment visit, the Last Visit, the End of Study telephone call, and to return to the clinic for the study planned Week 14 visit (unless consent is withdrawn). During the open-label extension, subjects who received NAL ER will continue on NAL ER for a total of 38 additional weeks (total treatment duration 52 weeks including titration) and subjects who received placebo will

crossover to NAL ER for a total of 38 weeks (including titration). Upon discontinuation of investigational product, all subjects will complete the 2-week off-treatment and safety follow-up period, regardless of when and why the subject discontinued study treatment, unless they withdraw consent. In addition, a final follow-up itch and safety assessment will be made via the End of Study telephone call 4 weeks after the last dose of investigational product. The total planned study duration from randomization through to the last telephone contact is 56 weeks.

Approximately 360 subjects with diagnosed PN will be randomized (1:1) to one of the following treatment arms:

Arm 1: Blinded active titration over 2 weeks (to achieve a final NAL ER dose of 162 mg) followed by 162 mg BID for 12 weeks with continuation into the extension titration period (blinded), and the open-label fixed-dose period, followed by a 2-week off-treatment safety follow-up period and a final telephone contact, for itch and safety assessment, 4 weeks after investigational product discontinuation.

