13.4.6.4 Interim Analysis (Adaptive Sample Size Re-estimation)

As described below, an adaptive mid-course Sample Size Re-Estimation (SSRE) procedure was introduced in Amendment 2, Protocol v3.1, when less than 10 subjects had been randomized. The analysis was to be performed after 50% of subjects (N=120) had either completed the Week 14 primary endpoint assessment or terminated the study early. Due to COVID 19-related delays, and because the key boundary for the lower margin of the SSRE did not differ if conducted at 45% of subjects, the SSRE was performed based on the Week 14 data for 109 subjects (including pre-Week 14 discontinuations). The analysis was performed as planned by a single, external, unblinded statistician, and was presented and discussed at a closed session of the study DSMB (July 9, 2020). Based on the DSMB's recommendation, the sample size for this study is being increased to 360 subjects since the SSRE conditional power fell within the 'promising zone' as defined by Mehta and Pocock.³³

Description of Pre-specified SSRE Procedures: The sample size re-estimation will be performed by one unblinded study statistician, who does not have a decision-making role in the trial; no one else, including Sponsor or clinical team members, had access or saw the unblinded data in the Data Monitoring Committee (DMC). The communication plan from the DMC is to report one of the following statements based on the conditional power results: 1) "carry on"; 2) "increase sample size to XXX"; or 3) "stop the study due to unfavorable safety and/or efficacy concern." Details about the DMC and the data monitoring procedures are specified in the DMC charter. When 50% of the subjects have provided the Week 14 primary endpoint data or have terminated the study and the data are considered "lockable" by data management, the data file will be provided with limited access to the unblinded statistician in the DMC; the proportion of responders will be estimated; and the conditional power (CP) will be calculated. Given that the interim analysis is to be performed at 50% of the initial sample size (120 subjects), the targeted power is 90%, and the maximum allowable sample size is set at 1.5 times the initial sample size

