ITT		Intent To Treat
IWRS		Interactive Web Response System
LOCF		Last Observation Carried Forward
MAR		Missing at Random
MCMC		Markov Chain Monte Carlo
MedDRA		Medical Dictionary for Regulatory Activities
MI		Multiple Imputation
MMRM		Mixed Model for Repeated Measurements
MVN		Multivariate Normal

OC	Observed Cases
OR	Odds Ratio
PAS	Prurigo Activity Score
PBI-P	Patient Benefit Index, Pruritus
PCS	Potentially Clinically Significant
PMH	Past Medical History
PNQ	Patients Need Questionnaire
PN	Prurigo Nodularis
PP	Per Protocol
PROMIS	Patient-Reported Outcomes Measurement Information System
PT	Preferred Term
Q1	Lower Quartile
Q3	Upper Quartile
QLS	Quality of Life Scale
SAE	Serious Adverse Event
SAP	Statistical Analysis Plan
SD	Standard Deviation
SDTM	Study Data Tabulation Model
SI	Standard International
SOC	System Organ Class
SOP	Standard Operating Procedure
SOWS	Subjective Opiate Withdrawal Scale
SSP	Study Specific Procedure
TEAE	Treatment Emergent Adverse Event
TFLs	Tables, Figures and Listings
ULN	Upper Limit of Normal
WI-NRS	Worst Itch Numerical Rating Scale
WOCF	Worst Observation Carried Forward

I. INTRODUCTION

The purpose of this Statistical Analysis Plan (SAP) is to provide detailed descriptions of the statistical methods, data derivations, and data displays for study protocol TR11 “A Phase 2b/3, Randomized, Double-Blind, Placebo-Controlled, 2-Arm, Efficacy, and Safety Study in Prurigo Nodularis with Nalbuphine ER Tablets for Pruritus Relief Through Itch Scratch Modulation (PRISM Study)” dated 14 March 2019 for final analysis. The table of contents and templates for the TFLs will be produced in a separate document.

Any deviations from this SAP will be described and justified in the Clinical Study Report (CSR). The preparation of this SAP has been based on International Conference on Harmonization (ICH) E9 and ICH E9¹ guidelines.

All data analyses and generation of TFLs will be performed using SAS 9.4[®] or higher.

II. STUDY OBJECTIVES

A. Primary objective

To evaluate the effect of Nalbuphine Extended-Release tablets (NAL ER) on itch as assessed by the percentage of Responders ('response' is defined as a ≥ 4 -point reduction in the 7-day average Worst Itch Numerical Rating Scale [WI-NRS]).

B. Secondary objectives

The secondary objectives of this study are designed to establish proof of principle and are as follows:

Key secondary objectives:

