- To evaluate the effect of NAL ER on itch-related quality of life as assessed by the ItchyQoL total score.
- To evaluate the effect of NAL ER on Prurigo Nodularis (PN) skin lesions as assessed by the Prurigo Activity Score (PAS) Question 5a.
- To evaluate the effect of NAL ER on sleep as assessed by the PROMIS Sleep Disturbance Short Form 8a.

Other secondary objectives:

- To evaluate the effect of NAL ER on itch as assessed by the mean change in WI-NRS.
- To evaluate the benefit to subjects of NAL ER using the Patient Benefit Index, pruritus version (PBI-P).
- To evaluate the safety and tolerability of NAL ER.
- To assess the PK of nalbuphine and its metabolites.

III. STUDY DESIGN

A. General study design

This is a randomized, double-blind, placebo-controlled, 2-arm study, with an open-label extension period following double-blind treatment, to investigate NAL ER tablets' anti-pruritic efficacy and

safety. Subjects will be randomized to NAL ER (2-week titration followed by 162-mg BID for 12 weeks) or matching placebo (14 weeks duration), with the primary endpoint evaluation at Week 14. If permanent discontinuation of investigational product occurs anytime between Day 1 and the Week 14 visit, the subject must complete the off-treatment visit and procedures, and must return to the clinic for ALL remaining study evaluation visits up to and including the Week 14 visit. During the open-label extension, subjects who received NAL ER will continue on NAL ER for a total of 38 additional weeks (total treatment duration 52 weeks including titration) and subjects who received placebo will crossover to NAL ER for a total of 38 weeks (including titration). Upon discontinuation of investigational product, all subjects will complete a 2-week off-treatment safety follow-up period, regardless of when and why the subject discontinued study treatment unless they withdraw consent. In addition, a final follow-up itch and safety assessment will be made via phone call 4 weeks after the last dose of investigational product. The total planned study duration from randomization through the last phone contact is 56 weeks.

Approximately 240 subjects with diagnosed PN will be randomized (1:1) to one of the following treatment arms:

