Arm 1: Blinded active titration over 2 weeks (to achieve a final NAL ER dose of 162 mg) followed by 162-mg BID for 12 weeks with continuation into the extension titration period (blinded), and the open-label fixed-dose period, followed by a 2-week off-treatment safety follow-up period and a final phone contact, for itch and safety assessment, 4 weeks after investigational product discontinuation.

[figure not shown]
Arm 2: Placebo “titration” over 2 weeks followed by placebo BID for 12 weeks with continuation into the extension titration period (blinded; to achieve a final NAL ER dose of 162 mg) and the open-label fixed-dose period (NAL ER 162 mg), followed by a 2-week off-treatment safety follow-up period and a final phone contact, for itch and safety assessment, 4 weeks after investigational product discontinuation.

An interim sample size re-estimation will occur once 50% (120) of the subjects have either completed the Week 14 primary endpoint assessment or terminated the study early. A maximum of 360 subjects total may be enrolled, dependent upon the results of the re-estimation.

After Study Week 28, an elective dose reduction to NAL ER 108 mg BID may be considered for subjects who achieve a confirmed WI-NRS ≤ 3 and visible lesion healing (as assessed by an improvement of at least 1 category in the PAS lesion healing activity score). The decision to dose reduce is at the discretion of the Investigator and the subject, but once this dosing has started, no re-escalation will be permitted.

The study design schematic is presented in Figure 1.

Figure 1 Study Design

BID: twice daily; D = day; NAL ER: Nalbuphine 162-mg extended release; WI-NRS: Worst Itch Numerical Rating Scale; W = week.

B. Randomization and blinding

Randomization will be performed by an IVRS/IWRS. Upon confirmation of eligibility by the study site, subjects will be randomized in a 1:1 ratio to either Arm 1 or Arm 2.

C. Study treatments and assessments

Double-blind Treatment Period

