5. SAMPLE SIZE AND POWER

The planned sample size of approximately 240 subjects (120 per group) is based on assumed responder percentages for placebo and NAL ER of 25% and 45%, respectively. These responder percentages represent estimates based on the Week 10 data from the TR03 study. Power is set at 90% with a 2-sided significance level of 0.05.

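### The final SAP still presents 240 subjects, 90% power and a future interim at 120 as the current plan, although the trial randomises about 360 after an interim done at 109

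*SAP*

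**What the plan says.** **SAP Final 2.1 (1 June 2022)**

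- The Introduction ties the plan to a protocol "dated 14 March 2019 for final analysis", which is Version 3.1.
- Section III.A: "Approximately 240 subjects with diagnosed PN will be randomized (1:1", and then "An interim sample size re-estimation will occur once 50% (120) of the subjects" have reached Week 14 or left the study. It adds that enrolment may rise to a maximum of 360, depending on the result.
- Section 5: "The planned sample size of approximately 240 subjects (120 per group) is based on assumed responder percentages", with the rates given as "assumed responder percentages for placebo and NAL ER of 25% and 45%, respectively". It continues: "Power is set at 90% with a 2-sided significance level of 0.05".
- Section 5.2 adds 80% power at 240 if the NAL ER rate is 41.8%. Sections 5.2 and 8.8.1 give the promising-zone rule: interim at 120, lower conditional power cut-off 41%, at most 180 per group. Both put the interim in the future.
- Section 9 (changes from the protocol) and Section 11 (version history) mention neither the increase nor the interim as performed.

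**Protocol Version 7 (21 July 2021)**

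- Section 9.1.1: "Approximately 360 subjects with diagnosed PN will be randomized (1:1".
- Section 13.4.6.4: "the SSRE was performed based on the Week 14 data for 109 subjects". The reason given is COVID-19 delay, with a statement that the lower boundary was the same at 45% of subjects.
- Section 13.1 calls 240 the original planned size.

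**The concern.** The SAP is the later document and the one called final. The DSMB saw the interim result on 9 July 2020, nearly 23 months before the SAP's date. A reader of the SAP alone cannot tell how many subjects were to be analysed, whether the interim took place, or at what information fraction.

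Two things depend on those facts. One is the power statement, which describes a size the trial no longer has. The other is the justification for an unweighted final test at 0.05. The SAP derives it from an interim at 50% of 240, whereas the interim took place at 109/240 = 45.4%. If the cut-off depended strongly on timing, the stated premise for alpha control would not match the trial.

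The outdated base also touches one analysis rule. The intercurrent-event list in SAP 8.6.1.3 names antihistamines, topical or systemic, and sets efficacy data to missing after such events. Version 7 admits subjects on a stable dose of systemic antihistamines (exclusion criterion 22 and Table-3). Read literally, the SAP rule could remove data from subjects whose use was permitted.

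**Working it through.** **Inputs.** Two-sided alpha 0.05, placebo rate p0 = 0.25, NAL ER rate p1 = 0.45, 1:1 allocation, 240 subjects, and the 41.8% alternative (SAP 5 and 5.2). Size 360 and interim at 109 (Protocol 9.1.1 and 13.4.6.4). No dropout inflation is stated.

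**Step 1: reproduce the SAP's size.** With p̄ = 0.35 and pooled null variance,

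n per arm = [1.96·√(2p̄(1−p̄)) + 1.2816·√(p0(1−p0) + p1(1−p1))]² / (p1−p0)²
= (1.3221 + 0.8452)² / 0.04 = 117.4, so 118 per arm, 236 in total.

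The SAP gives 234 without site and 240 after its site-adjusted runs. Both agree to within 3%.

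**Step 2: power.** Power = Φ{[(p1−p0) − 1.96·SE0] / SE1}, where SE0 = √(2p̄(1−p̄)/n) and SE1 = √([p0(1−p0) + p1(1−p1)]/n).

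| n per arm | Rates | SE0 | SE1 | z | Power | SAP states |
|---|---|---|---|---|---|---|
| 120 | 25% v 45% | 0.0616 | 0.0602 | 1.317 | 90.6% | 90% |
| 120 | 25% v 41.8% | 0.0609 | 0.0599 | 0.812 | 79.2% | 80% |
| 180 | 25% v 45% | 0.0503 | 0.0492 | 2.064 | 98.0% | none |
| 180 | 25% v 41.8% | 0.0497 | 0.0489 | 1.442 | 92.5% | none |

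At 180 per arm, 80% and 90% power are reached at NAL ER rates of about 38.7% and 41.0%.

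**Step 3: does the cut-off move with an interim at 109?** With N = 240, N* = 360, interim size n1 and interim statistic z1, the critical value that preserves alpha is

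b = [√((N*−n1)/(N−n1))·(1.96√N − z1√n1) + z1√n1] / √N*.

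The conventional test is safe where b ≤ 1.96. Conditional power under the current trend is

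CP = 1 − Φ[(1.96√N − z1√n1)/√(N−n1) − z1√(N−n1)/√n1].

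- n1 = 120: b = 1.96 at z1 = 1.268, so CP = 1 − Φ(1.504 − 1.268) = 40.7%.
- n1 = 109: b = 1.96 at z1 = 1.207, so CP = 1 − Φ(1.552 − 1.323) = 41.0%.

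Both agree with the stated 41% and with the protocol's remark that the boundary did not differ.

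**Step 4: how far the 98.0% can be read.** It assumes a fixed sample and a true 25% v 45%. The documents do not give the interim result beyond its falling in the promising zone. Assume current-trend conditional power, an equal split of the 109 and an observed placebo rate of 25%. The planned 20-point difference would then have given z1 = 0.20/√(2·0.35·0.65/54.5) = 2.19 and conditional power of about 96%, above the 90% upper limit. The zone from 41% to 90% corresponds to observed differences of roughly 11 to 18 points. If those were the true differences, fixed-sample power at 360 would be about 59% to 95%.

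**The case against.** The strongest reply is that nothing here is miscalculated and nothing was concealed. The 240 and the 90% are right for the design they describe, and the current protocol keeps the same figures, labelled as original. The SAP states the 360 ceiling and the rule leading to it, so the trial followed a pre-specified branch. The protocol discloses the interim at 109 with its date and reason. No test, estimate or alpha level changes. All of this stands and limits the point to consistency. It does not remove it: a final SAP should not describe a completed interim as still to come, and the contingency wording does not say which branch was taken.

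A reader might infer three stronger things that the documents do not support:

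- **That the trial is underpowered or its power wrong.** Step 2 reproduces the stated figures, and the larger size raises power on the same assumptions.
- **That the earlier interim undermines alpha control.** Step 3 shows a cut-off of 41.0% against 40.7%.
- **That the per-protocol criteria in SAP 6.3 carry outdated numbers.** The list takes exclusions 16, 17 and 19 to 25. It skips 18, the criterion that Version 7 marks as not applicable, and the protocol's change summary says the numbering was kept when 18 was removed. The list fits Version 7.

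Nor is the whole SAP built on Version 3.1. It carries later content, such as the six-week screening period and the item 5b example for down-titration.

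On antihistamines, one can argue that data are lost only after an event starts, and that the question posed concerns adding medication, so stable background use is not caught. That reading is reasonable, but the list does not say so.

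**Conclusion.** The point holds as an inconsistency. SAP Final 2.1 presents a superseded size, its power and a future interim as current, cites a protocol from 2019, and leaves the increase out of both its list of changes and its version history. The gap is 240 against about 360 randomised, and 120 against 109 at the interim. On the SAP's own assumptions, power moves from about 90% to 98.0%.

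That last figure rests on the original 25% v 45% and ignores the adaptation. It should not be read as the trial's power given what the interim showed. The cut-off check assumes the standard current-trend conditional power formula, which the documents do not write out but whose result they match.

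The antihistamine mismatch is real but confined to the prohibited-medication sensitivity analyses, which SAP 8.6.3 extends to PAS item 5a.

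**What to change.** 1. In SAP III.A, 5 (with 5.2) and 8.8.1, label 240 subjects, 90% power, 80% power at 41.8% and the interim at 120 as the original plan.
2. In the same places, state that the re-estimation was done at 109 of 240 with the lower cut-off still 41%, and that the size was increased to 360 (180 per arm). Record this in Section 11.
3. Add power at 360, marked as fixed-sample power under the original assumptions and ignoring the adaptation: about 98.0% for 25% v 45%, 92.5% for 25% v 41.8%, and 80% and 90% at NAL ER rates of about 38.7% and 41.0%. Say that these come from a two-proportion test without site, unlike the SAP's 240.
4. In the Introduction, cite Protocol Version 7 as governing.
5. In SAP 8.6.1.3, limit the systemic-antihistamine item to use that Version 7 does not permit, so that subjects on permitted stable doses keep their data.

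Items 1 to 4 are wording only. Item 5 is one phrase and the matching selection of medication records. If the database is already locked, items 1 to 4 can go in the clinical study report, where the SAP says deviations are to be described; item 5 should then be reported there as a clarification with its date.
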